3 STUDY DESIGN AND PLAN

3.1 Overall Study Design and Plan

This is a Phase 1, single-center, open-label study of MGD014 in PLWH infection on stable ART. PLWH who began ART during either chronic HIV-1 infection or acute HIV-1 infection with plasma HIV-1 RNA < 50 copies/mL for 24 months prior to screening will be consented to the study. The screening procedures and initial evaluations that follow the consent determine eligibility for study entry. Eligible participants continue their baseline ART regimens throughout the study and receive either one infusion (Part 1) or an IV infusion once every 2 weeks (Q2W) for a total of three infusions of 300 mcg/kg of MGD014 for 4 weeks (Part 2), as briefly described below. See **CP-MGD014-01 Protocol Section 4.2** and **4.3** for further details.

3.2 Part 1 – Dose Escalation Phase

Single Ascending Dose (Cohort 1 & 2: n= 1 to 4 participants per dose cohort; Cohorts 3-8: n= 3 to 6 participants per dose cohort). Part 1 is a single ascending dose study with a 1+3 design for cohorts 1 and 2, and a 3+3 design with staggered accrual for cohorts 3-8, with an aim of determining the safety, PK, and pharmacodynamics (PD) of ascending doses up to either the Optimal Biologic Dose (OBD) or the maximum administered dose. *During Part 1, the OBD is identified. The OBD is defined as the MGD014 dose that does not exceed the MTD and achieves either maximum receptor occupancy of CD3 >95% in all participants within the dose cohort, or is at the maximum administered dose (MAD) level of 300 µg/kg.*

Part 1 has 8 unique dose cohorts: 0.1, 0.3, 1.0, 3.0, 10, 30, 100, and 300 µg/kg. For cohorts 1 and 2, each dose cohort will consist of 1 participant, unless a dose limiting toxicity (DLT) is encountered, which will prompt expansion of the dose cohort to an additional 3 participants. A 2-week DLT period will be observed prior to escalation of the dose to the next dose cohort level. For dose cohorts 3-8, each dose cohort will consist of 3 participants, with at least 24 hours between the dosing of each participant within the cohort. If a DLT is experienced in one of the three participants, the dose cohort will be expanded to 3 additional participants. Following infusions, the study will monitor safety parameters as well as the effects of MGD014 on clinical chemistry, hematology, serum cytokines, T-cell phenotype, T cell binding, PK, ADA, and single copy assay (SCA).

3.3 Part 2 – Multi-Dose Cohort Expansion Phase

Part 2 is a multi-dose expansion cohort with repeat administrations of MGD014 at 300 mcg/kg. Up to 6 patients will be enrolled in Part 2.

Participants previously enrolled in and having completed Part 1 may be considered for enrollment in Part 2, provided they continue to meet all eligibility criteria, did not experience any DLT in Part 1, and do not have any detectable ADA at the completion of Part 1.

In Part 2, additional optional assessments on the effects of MGD014 on HIV-1 latent infection parameters include measurements of resting cell infection (frequency of persistent infection of resting CD4 T cells) by quantitative viral outgrowth assay (QVOA), latency clearance assay (LCA) to assess the impact of MGD014 administration on MGD014-mediated clearance activity in vitro, SCA, and T-cell phenotype and functional properties.

4 STATISTICAL METHODOLOGY

4.1 General Considerations

The majority of the statistical summaries for this Phase 1 trial will be descriptive. Summary statistics will consist of absolute and relative frequencies of each category of discrete variables of means, standard deviations, coefficient of variations, medians, and minimum and maximum values of continuous variables.

All data summaries and tabulations will be conducted using SAS® software Version 9.4 or higher.

4.2 Missing Data

Data that are reported as missing will be treated as missing in all data summaries. Imputation rules for partially recorded dates, in case that the complete dates are required to carry out an analysis, will be provided in the Statistical Programming Plan (SPP). In descriptive summaries for safety, observations that are spurious (extreme relative to the majority of the data) will not be altered or removed from the summary.

4.3 Determination of Sample Size

The number of participants is not based on statistical power calculations. A 1+3 design is utilized in the first two dose levels of Part 1 because the starting dose is considered biologically conservative and the anticipated risk of DLT is low. A 3+3 design is used for dose cohorts 3-8. The total sample size of Part 1 is at least 20, but will depend upon the occurrence of DLTs and potential need for expanded dose level cohorts (see **CP-MGD014-01 Protocol Section 4.2.1**). Part 2 of the study will have up to six (n=6) participants. This study overall plans to have approximately 26 HIV-1 infected, ART suppressed participants in total (Part 1 + Part 2). No inferential statistics will be calculated in Part 1. This sample size is considered biologically sufficient to evaluate the primary objective of this study (first in human evaluation of safety and tolerability of MGD014).

4.4 Analysis Populations

All participants who receive any MGD014 infusion will be included in the safety data sets. Participants enrolled in the Part 1 single-dose cohort will contribute to analysis of the OBD and MAD or MTD. Participants enrolled in the Part 2 multi-dose cohort will contribute to multi-dose safety, PK, and PD analyses.

4.5 Demographics and Baseline Characteristics

Participant disposition, demographics, baseline characteristics, disease history, and medical history will be summarized using descriptive statistics. Key demographic and baseline characteristics include biological sex, race/ethnicity, age, baseline ART regimen, years on ART, and nadir CD4.

4.6 Study Drug Exposure and Concomitant Medications

Study drug exposure and concomitant medications will be summarized by descriptive statistics. The summary of study drug exposure will include descriptive statistics as well as frequency counts for the number of doses received, the total dose actually administered as well as the total dose intended, and the dose intensity which is calculated as percentage of total dose actually administered divided by total dose intended during study treatment period.

Duration of study treatment (months) will be calculated as:

- (date decided to discontinue treatment – date of first dose + 1)/(365.25/12) for patients who have discontinued treatment.
- (date of data cutoff – date of first dose + 1)/(365.25/12) for patients whose treatment is ongoing.

The summary of concomitant medications will include the number and percentage of patients who receive any concomitant medications as well as each concomitant medication by drug class.

4.7 Protocol Deviations

Major protocol deviations will be identified prior to database lock for final analysis and will be listed and summarized.

4.8 Safety Endpoints and Analyses

4.8.1 Adverse Events

Adverse events will be coded to the Medical Dictionary for Regulatory Activities (MedDRA). Events prior to treatment (e.g., due to study-related procedure) will be listed separately in an appendix to the final CSR.

The following tables of AE data will be created to summarize the number and percent of participants who experience at least one event of each of the following types:

- All AEs
- All study drug-related AEs
- Study drug related AEs by severity grade
- AEs by severity grade
- All SAEs (this may be a listing if there are few events)
- Study drug-related SAEs
- Fatal AEs (this may be a listing if there are few events)

- AEs that result in study discontinuation
- AEs that lead to withdrawal of study drug
- AEs categorized as AESI and/or IREs
- AEs with severity grade 3 or greater
- Study drug-related AEs with severity grade 3 or greater

All of these tables will display the number and percent of participants that experience the given event and will display events by System Organ Class (SOC) and Preferred Term (PT). Events will be displayed alphabetically for SOC and in descending order of overall PT incidence within each SOC.

4.8.2 Laboratory Values and Analyses

Summaries of abnormal laboratory values will display descriptive statistics for numerically quantified labs. Summaries will be grouped by lab panel (e.g., hematology, blood chemistry, and urinalysis) and will be displayed by visit for each lab parameter. Graphs of mean values over time or individual values at each time point may be used. Mean change from baseline may also be graphed. Graphs of individual values are preferred when feasible due to the small sample size of this study.

In cases where an abnormality resulted in a repeat lab test, the repeat value will be used for the summaries. A list of repeated labs including original values and repeat values will be included.

Shift tables will be used to display the number and percent of participants who have a shift in their lab values from normal at baseline to each post-baseline visit by severity grade.

4.8.3 Other Safety Endpoints and Analyses

Electrocardiograms will be collected and analyzed for evidence of cardiac toxicity, especially prolongation of QT interval. Vital signs will be summarized with descriptive statistics at each visit and time point where they are collected.

4.9 Efficacy Endpoints and Analyses

The following efficacy endpoints are exploratory and only apply to Part 2 patients. The described analyses of these endpoints below are optional and may not be performed if less than 6 patients are eventually enrolled to Part 2.

4.9.1 Quantitative Viral Outgrowth Assay

For participants who completed the optional leukapheresis, a comparison of pre-MGD014 and post-MGD014 frequency of HIV infection per million resting CD4 T cells will be

performed using a non-parametric 2-sided exact sign test to assess whether or not a significant decrease of infectious units per million (IUPM) CD4 T cells is observed. The primary comparison will be between the leukapheresis taken at baseline and approximately 2 weeks following the last MGD014 infusion in Part 2 (at Day 42 ± 2 weeks). The sign test used for this analysis makes minimal statistical assumptions and is based solely upon whether each participant is observed to have a decrease in IUPM following MGD014 treatment. Results will be presented as the proportion with decreased IUPM and the corresponding confidence interval (CI). If the observed proportion with decreased IUPM is 100% (6/6 participants), the corresponding 95% CI will span from [0.541, 1.000]; this CI would exclude a null hypothesis of no change (H_0 : probability of decrease=0.50).

Table 1 Precision calculations for QVOA analysis

Number of participants with decrease in IUPM	Binomial 95% CI (Clopper-Pearson)
6 of 6 (100%)	[0.541, 1.000]
5 of 6 (83%)	[0.359, 0.996]

IUPM=infectious units per million CI=confidence interval

4.9.2 Single Copy Assay

For participants who completed the optional leukapheresis, a comparison of pre-MGD014 and post-MGD014 measurements of residual low-level HIV-1 viremia quantified by SCA using a nonparametric 2-sided exact sign test will be performed to assess whether or not a significant decrease in plasma HIV-1 viremia is observed. Left-censored observations (SCA < 1 copy) are anticipated and the sample size is six (6) participants. Based on background data from the AIDS clinical trials group (ACTG) trial A5244, we assume a 10% probability that participants (with plasma HIV-1 RNA <50 copies/mL at screening, per eligibility) will have a SCA measurement below the limit of detection (<1 copy) at the pre-MGD014 measurement; it is unknown how large of an effect MGD014 will have upon SCA levels post-therapy. The precision calculations provided above in the QVOA analysis section apply here, i.e., if the observed proportion with decreased low-level HIV-1 viremia as measured by SCA is 100% (6/6 participants) the corresponding 95% CI will span from [0.541, 1.000] and the null hypothesis can be rejected.

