14.5.2 Single Copy Assay

For participants who completed the optional leukapheresis, a comparison of pre-MGD014 and post-MGD014 measurements of residual low-level HIV-1 viremia quantified by SCA using a nonparametric 2-sided exact sign test will be performed to assess whether or not a significant decrease in plasma HIV-1 viremia is observed. Left-censored observations (SCA < 1 copy) are anticipated and the sample size is six (6) participants. Based on background data from the AIDS Clinical Trials Group (ACTG) trial A5244, we assume a 10% probability that participants (with plasma HIV-1 RNA <50 copies/mL at screening, per eligibility) will have a SCA measurement below the limit of detection (<1 copy) at the pre-MGD014 measurement [54]; it is unknown how large of an effect MGD014 will have upon SCA levels post-therapy. The precision calculations provided above in the QVOA analysis section apply here, i.e., if the observed proportion with decreased low-level HIV-1 viremia as measured by SCA is 100% (6/6 participants) the corresponding 95% CI will span from [0.541, 1.000] and the null hypothesis can be rejected.

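### The Part 2 SCA sign test is limited to completers of an optional leukapheresis that it does not need, and its precision statement omits the 53% cap implied by the plan's own 10% undetectable-baseline assumption

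*SAP*

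**What the plan says.** The analysis set is fixed in the opening of SAP 4.9.2: "For participants who completed the optional leukapheresis, a comparison of pre-MGD014 and post-MGD014 measurements of residual low-level HIV-1 viremia quantified by SCA", by a two-sided exact sign test. Protocol 14.5.2 has the same condition: "For participants who completed the optional leukapheresis, a comparison of pre-MGD014 and post-MGD014 measurements of residual low-level HIV-1 viremia". Protocol 11.1 makes both efficacy markers, QVOA and SCA, depend on consent to leukapheresis. In Protocol Appendix 1, the Part 2 SCA row carries footnote mark 23, the optional-leukapheresis footnote.

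On numbers, SAP 4.9.2 says: "Left-censored observations (SCA < 1 copy) are anticipated and the sample size is six (6) participants". It continues "we assume a 10% probability that participants" will have a value "below the limit of detection (<1 copy) at the pre-MGD014 measurement". It then says "The precision calculations provided above in the QVOA analysis section apply here", and adds that six decreases out of six give [0.541, 1.000] and reject the null. The imported Table 1 (SAP 4.9.1) has two rows, 6/6 and 5/6. According to SAP 4.9.1 the sign test "is based solely upon whether each participant is observed to have a decrease in IUPM following MGD014 treatment". SAP 4.9 calls these endpoints exploratory and says the analyses "may not be performed if less than 6 patients are eventually enrolled to Part 2".

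On specimens, Protocol 9.16 sends plasma SCA samples in batches to an outside laboratory and keeps resting CD4 cell samples at the site. Footnote 23 says only that the QVOA samples come from the leukapheresis product. In Part 1, SCA is followed after infusion (Protocol 4.2), yet the only leukapheresis there precedes dosing (Protocol 9.10).

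On timing, Protocol 4.3 (Part 2, Step 1) describes two pre-dose time points for SCA. The Part 2 schedule, as far as it can be read, shows one pre-dose draw (Visit 2) and later draws at Days 1, 42 and 77. That table may be damaged in extraction. The SAP names neither a baseline rule nor a post-dose visit for SCA.

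**The concern.** The leukapheresis condition makes sense for QVOA, whose cells come from that procedure. For SCA the documents give no reason for it, and it can only reduce the number of pairs in a test that cannot spare any. The gate in SAP 4.9 counts patients enrolled, not pairs available. Replacement under Protocol 5.3.1 covers withdrawal, not refusal of an optional procedure or an undetectable baseline.

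The 10% assumption and the precision statement also stand next to each other without being connected. A participant below 1 copy before dosing cannot be observed to decrease, so the assumption bears directly on whether six out of six can be reached. A reader who does not see this could take a non-significant SCA result as evidence of no effect when significance was never attainable.

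**Working it through.** **Inputs.** Pairs: at most six (SAP 3.3, 4.9.2). Test: two-sided exact sign test, null probability of decrease 0.50 (SAP 4.9.1, 4.9.2). Level: two-sided 0.05 (SAP 4.9.3). Chance of an undetectable baseline: 10% per participant (SAP 4.9.2). Leukapheresis uptake: not given.

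**Step 1: reproduce the plan's figures.** With n decreases out of n, the lower Clopper-Pearson limit is 0.025^(1/n). For n = 6 this is 0.541, so the interval is [0.541, 1.000]. For 5/6 the interval is [0.359, 0.996]. Both match Table 1.

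**Step 2: which results show a significant decrease?** The two-sided p is twice the upper binomial tail at 0.5.
- 6/6: 2 × 1/64 = 0.031, significant.
- 5/6: 2 × 7/64 = 0.219, not significant.
- 5/5: 2 × 1/32 = 0.0625, not significant; interval [0.478, 1.000].
- 4/4: 2 × 1/16 = 0.125, not significant.

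With six or fewer pairs only 6/6 suffices. If replacements led to seven or eight pairs, all would still have to decrease (6/7 gives 2 × 8/128 = 0.125; 7/8 gives 2 × 9/256 = 0.070).

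**Step 3: effect of the leukapheresis condition.** With six enrolled and one refusal, at most five pairs remain. The smallest possible p is 0.0625, so the chance of a significant decrease is zero whatever the drug does. No uptake assumption is needed.

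**Step 4: effect of the 10% assumption, with all six analysed.** One undetectable baseline leaves at best 5/6 (p = 0.219) if that participant stays in the denominator, or 5/5 (p = 0.0625) if dropped. Six out of six therefore requires six detectable baselines:
- P(all six detectable) = 0.9^6 = 0.531.
- P(exactly five) = 6 × 0.9^5 × 0.1 = 0.354.
- P(four or fewer) = 1 − 0.531 − 0.354 = 0.114 (from unrounded values).

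If the rate were 5% or 20% instead, the cap would be 0.95^6 = 0.735 or 0.8^6 = 0.262.

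**Step 5: two pre-dose values.** If a second pre-dose value is collected and either detectable value suffices, the chance that both are undetectable lies between 0.10 (the two always agree) and 0.10 × 0.10 = 0.01 (independent). The cap then lies between 0.9^6 = 0.531 and 0.99^6 = 0.941. The documents do not give the dependence.

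**Step 6: the other direction.** No decreases out of six gives 2 × 1/64 = 0.031. An undetectable baseline rules out a significant decrease but not a significant increase.

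**The case against.** The strongest reply is that the plan states nothing false. The sentence on rejection is conditional on 6/6, the intervals are right, left-censoring and the 10% are disclosed in the same paragraph, and SAP 4.3 says the sample size does not rest on power. The endpoint is exploratory, its analysis is optional, and under SAP 2.3 exploratory results may not enter the study report. All of this stands. The 53% is information the plan omits, not an error it makes.

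A reader might infer that the SAP gives only the best case for SCA. It does not: it imports the QVOA calculations, and Table 1 includes the 5/6 row, whose interval contains 0.50.

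A reader might also infer that data already in hand would be thrown away. The documents do not establish this. SCA in Part 2 is described as optional (Protocol 4.3), and its schedule row carries the leukapheresis footnote, so samples from those who decline may never be tested. Removing the condition may therefore change sample testing as well as analysis.

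Finally, two pre-dose values might suggest a risk of inflated false positives from choosing the higher one. No passage proposes that choice. The supported point is narrower: Protocol 4.3 and the schedule differ on the number of pre-dose draws, and the SAP names no rule.

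**Conclusion.** The point holds as a minor improvement. The leukapheresis condition has no stated basis for a plasma assay, and with six enrolled a single refusal removes any chance of a significant decrease. That conclusion needs only the test, the level and the enrolment limit.

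Separately, the plan's own 10% caps the chance of six out of six at 53% with one baseline value. The cap assumes independence between participants, complete follow-up, and an observed fall in every participant with a detectable baseline, so the real chance would be lower. A cap as high as 94% would need a second pre-dose value, a rule that either detectable value suffices, and independence of the two.

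It might seem to follow that no test should be run when fewer than six baselines are detectable. That goes too far, because the planned test is two-sided and could still show an increase. The primary safety objective is unaffected.

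**What to change.** 1. Remove the leukapheresis condition for SCA in SAP 4.9.2 and Protocol 11.1 and 14.5.2, and take footnote mark 23 off the Part 2 SCA row. Analyse all Part 2 participants with pre- and post-dose plasma. Keep the condition for QVOA.
2. Add to SAP 4.9.2 that a significant decrease requires six decreases out of six, and that the 10% assumption caps the chance of this at 53% with a single baseline value (up to 94% only under the conditions of step 5).
3. Reconcile Protocol 4.3 with the Part 2 schedule on the number of pre-dose SCA draws. Name one baseline rule (the single value, or the log10 mean if two exist) and one post-dose visit, for example Day 42 as for QVOA.
4. Report a pair undetectable before and after as no observed decrease, in line with SAP 4.9.1, and give the number of such pairs. Do not read them as increases.
5. Keep the two-sided test. If fewer than six participants have a detectable baseline and a post-dose value, state that a significant decrease was unattainable. Report individual values and the proportion decreasing with its exact interval, and do not read the result as no effect.

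The cost is a protocol amendment with the submissions described in Protocol 16.1, a few more plasma SCA assays for those who decline leukapheresis, and a less favourable stated precision. No additional participants are needed.

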4.9.3 Exploratory Endpoints and Analyses

Additional exploratory endpoints are defined as changes in quantitative measures from baseline to post-MGD014 administration. Using a two-sided 0.05 significance level, 10,000 empirical simulations from a normal distribution with mean change equal to 2 standard deviations (SD) with n=6 evaluable participants achieved 86% power to detect a statistically significant change from baseline to post-infusion using an exact Wilcoxon signed-rank test (for paired data). Observed virologic and immunologic measurements may not be normally distributed or may be partially censored due to assay limits of quantification. A Wilcoxon signed-rank test will be used for continuous outcome measures when appropriate; otherwise, an exact sign test will be utilized. Potential immune correlates of antiviral impact will be

assessed graphically (e.g., scatter plots, correlate heat map) and estimated with a non-parametric rank based correlation method. Additionally, association between antiviral impact of MGD014 and baseline participant clinical characteristics, such as stage of HIV infection (acute vs. chronic) at initiation of ART, will also be described and examined. Correlation including one or more measures from the same participant may be assessed using Kendall's tau for clustered data [1]. Exploratory analyses will be conducted using a two-sided 0.05 significance level with no adjustment for multiplicity.

4.10 Pharmacokinetic Endpoints and Analyses

Geometric means and percent coefficients of variation may be reported for C_{max} , AUC, and C_{trough} ; arithmetic means and standard deviations may be reported for $t_{1/2}$, CL, and V_{ss} ; and medians, minimum, and maximum will be reported for T_{max} .

